## 15.0 Statistical Considerations

*15.1 Data Analysis Plan:*

Preliminary Analyses to Determine Covariates Needed for Primary Analyses. The purpose of collecting data on potential covariates is to identify variables that are correlated with both the independent variable (social buffering condition, sex, pubertal stage) and the primary outcome measures. Those covariates that are associated with the independent and outcome variables will be controlled for in the primary analyses. Those that are not will be used to describe the sample, but will not need to be included in the analyses to obtain unbiased estimates. For each potential covariate, we will conduct correlations or t-tests with pubertal stage, and t-tests, ANOVAs, or chi-square tests (as appropriate) with sex and condition. If data do not confirm to modeling assumptions, we will use nonparametric analogs instead.

Preliminary Analyses of Imaging Data to Yield Primary Outcome Measures: fMRI data will be analyzed in FSL software (version 5.0.10) to generate voxel-wise contrast maps. Mean signal values will be extracted from these maps in a priori regions of interest for every participant using the methods described below. These preliminary analyses are used to generate the fMRI outcome variables of interest. The values of these outcome variables for each participant will be used in the general statistical analyses described in the next section. In total, these preliminary analyses will yield 6 primary task-related outcome variables, and 6 primary connectivity-related outcome variables.

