### 15.3 Statistical Analysis of MRI and non-MRI Outcome Variables:

The following is a list of the analyses that we will perform on the outcome measures. They are classified as to whether they are the primary or mediational analyses. All statistical analyses will be performed in R.

The primary analyses will consist of a series of multiple regression models. For each dependent variable, variation in neural activity, cortisol response, and heart rate response, we will begin by testing the three-way interaction between social buffering condition, sex, and pubertal stage for all outcomes. If the three-way interaction is not significant, we will then examine all two-way interactions. If the two-way interactions are not significant, we will then examine main effects only models. If the three-way interaction is significant, we will not examine any other model. If condition is significant as an interaction or as a main effect, we will examine all pairwise comparisons using Tukey's Honestly Significant Difference test.

Multiplicity of testing. We will correct for multiple comparisons using the Benjamini-Hochberg (BH) correction. The BH method works by controlling the false discovery rate, and relative to the Bonferroni's correction is more powerful, while still adequately protecting against Type I error (Williams, Jones, & Tukey, 1999).

Mediational Analysis. When changes in activity of brain regions differ by condition or condition by pubertal status and we also see condition or condition by pubertal status differences for cortisol, or heart rate, then we will examine whether brain activity differences mediate the neuroendocrine or autonomic differences. This will be examined using path analysis, while controlling for covariates identified in the preliminary

covariate analysis, and will be estimated using the lavaan package in R (Rosseel, 2012).

The significance of all indirect effects will be assessed using bias-corrected 95% confidence intervals (Efron & Tibshirani, 1986), where confidence intervals that are non-overlapping with zero will be considered significant.

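### Indirect effects are called significant from separate unadjusted 95% intervals, and the plan does not tie its Benjamini-Hochberg step to them

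*Combined protocol and SAP*

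**What the plan says.** Section 15.3 covers two kinds of analysis: "They are classified as to whether they are the primary or mediational analyses". Its multiplicity paragraph comes after the primary regressions and before the mediation paragraph. It reads "We will correct for multiple comparisons using the Benjamini-Hochberg (BH) correction" and defines no family of tests.

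Mediation is conditional: "When changes in activity of brain regions differ by condition or condition by pubertal status and we also see" condition or condition-by-puberty "differences for cortisol, or heart rate, then we will examine whether brain activity differences mediate the neuroendocrine or autonomic differences". For the paths that enter, "The significance of all indirect effects will be assessed using bias-corrected 95% confidence intervals", and "confidence intervals that are non-overlapping with zero will be considered significant". No p-value, adjusted level or mediation family is given.

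On the candidate mediators, section 15.1 says that "these preliminary analyses will yield 6 primary task-related outcome variables, and 6 primary connectivity-related outcome variables".

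The status of mediation differs by place. Section 2.3 makes it Hypothesis #2. The mediation power paragraph in section 15.3 calls the analysis exploratory and counts rejections at an unadjusted alpha of .05.

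**The concern.** An indirect effect is a product of two links: condition to brain measure (a), and brain measure to physiology given condition (b). The entry condition looks at the condition effect on the brain measure and at the condition effect on physiology. It carries no information about b. Suppose condition changes both the brain and cortisol or heart rate, but by separate routes. Every affected path then enters, and all that stands between it and a claim of mediation is a test of b at a nominal 5%, repeated for each brain measure and outcome.

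This is not a remote case. Hypothesis #1 predicts condition effects on the brain measures, and the study is designed around a condition effect on physiology. An analyst who follows the written rule could report mediation from one interval among many although no brain measure influences cortisol or heart rate.

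**Working it through.** **1. The plan's own figures.** The mediation power paragraph gives no numeric power or effect size, so there is nothing to reproduce for this analysis. The neighbouring figure in section 15.2 does reproduce. With three conditions there are 2 numerator df and 23 predictors (12 covariates, 4 main-effect terms, 5 two-way terms, 2 three-way terms), so the denominator df are 200 - 23 - 1 = 176. At f² = 0.056 the power is 0.809. At n = 160 and f² = 0.070 it is 0.795. Both agree with the stated .80. They concern the primary regressions, not mediation.

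**2. How many paths.**
- Brain measures: 6 task + 6 connectivity = 12 (section 15.1).
- Physiological outcomes named for mediation: cortisol and heart rate = 2 (section 15.3).
- Ceiling per condition contrast: 12 × 2 = 24. If only the six activation measures count as mediators: 6 × 2 = 12.
- Three conditions (section 5.2) give two independent contrasts, so the ceiling for all 12 measures is 48.

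The number actually tested depends on how many measures pass the entry condition.

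**3. Simple benchmark.** With m independent tests at 5% and no true mediation, P(at least one false) = 1 - 0.95^m. This gives 0.098 for m = 2, 0.265 for m = 6, 0.460 for m = 12 and 0.708 for m = 24.

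**4. Simulation of the planned procedure.** Assumptions, none of which the documents supply: three equal arms; a parent effect of d = 0.8 on brain measures and on both physiological outcomes; inter-region correlation 0.3; b = 0 for every path; entry decided by BH on the omnibus condition tests; bias-corrected 95% bootstrap interval (1000 draws) for the parent-versus-none indirect effect. There were 500 to 1000 trials per setting, so Monte Carlo error is about 1 to 2 percentage points. The results at n = 200 were:

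| Brain measures affected | Mean paths entering | False rate per path | At least one false mediation | Same, with BH |
|---|---|---|---|---|
| 1 | 2.0 | 0.078 | 0.145 | 0.078 |
| 3 | 5.98 | 0.077 | 0.352 | 0.080 |
| 6 | 11.92 | 0.078 | 0.555 | 0.098 |
| 12 | 23.93 | 0.074 | 0.750 | 0.100 |

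Section 15.2 allows for 40 participants lost to movement, which leaves 160. Over n = 160 to 200 the uncorrected chance is about 14-18% with one region, 35-38% with three and 56% with six.

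The per-path rate exceeds 5% because the bias-corrected interval is mildly liberal. This explains why the simulated values lie above the benchmark in step 3. As a check, 1 - (1 - 0.078)² = 0.150 against 0.145 simulated, and 1 - (1 - 0.077)⁶ = 0.382 against 0.352. Correlation between paths lowers the simulated value.

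**5. Sensitivity with 12 measures, n = 200.**
- d = 0.5: 0.61 uncorrected, 0.06 with BH.
- d = 0.8, inter-region correlation 0: 0.85 and 0.12.
- d = 0.8, inter-region correlation 0.6: 0.62 and 0.08.
- No condition effect anywhere: the entry condition was met in 0.1% of trials and no false mediation occurred.

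BH was applied to p-values obtained by inverting the same bias-corrected bootstrap. When no path is truly mediated, every rejection is false, so the false discovery rate equals the chance of at least one false mediation and the BH target is 5%. The excess over 5% comes from the interval, not from BH.

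**The case against.** The strongest reply has four parts.

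- **BH already covers it.** A reader might infer that BH cannot apply to mediation because the rule uses intervals. The documents do not support that. The BH sentence is unrestricted, stands in a section that covers mediational analyses, and can be applied through bootstrap p-values. What stands against the reply is that the mediation rule is complete in itself: it names a fixed 95% level for all indirect effects, and the mediation power was taken at unadjusted .05. BH is possible but not specified.
- **The entry condition is a form of control.** This is right when condition has no effect, as step 5 shows, so a reading that there is no protection at all goes too far. It gives no protection when condition acts on brain and physiology without mediation.
- **The path count is a maximum.** This stands. The entry condition speaks of activity in brain regions, and the plan does not say whether connectivity measures are mediators or whether models hold one mediator or several. That is why the size is given for one, three and six regions.
- **The analysis is exploratory.** The power paragraph says so, and also warns that power is limited and that complete mediation could be concluded wrongly. If that label governs, unadjusted intervals are acceptable, but not a rule that calls them significant. Nor does the label agree with Hypothesis #2.

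**Conclusion.** The concern holds in a limited form. Followed literally, the plan calls each indirect effect significant from its own unadjusted interval, and the general BH sentence is not tied to these tests. Once paths enter, error across them is not controlled in the case where condition affects brain and physiology but brain activity does not mediate. Under the stated assumptions, the chance of at least one false mediation is about 14-18%, 35-38% and 56% with one, three and six affected regions. With BH it is about 6-10%.

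These sizes rest on assumed effects and correlations and on BH at entry. Larger figures apply only if all 12 measures are affected and all count as mediators; the 24 paths per contrast should not be read as the number that will be tested. The direction of the result does not depend on the particular values, provided that condition affects both brain and physiology.

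**What to change.** First reconcile section 2.3 (Hypothesis #2) with the mediation power paragraph in section 15.3 (exploratory), and state which status applies.

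- **If mediation is to support a claim about Hypothesis #2:** compute a bootstrap p-value for each indirect effect. Apply BH across all those examined, defined as brain measure × physiological outcome × condition contrast, including moderated paths. State whether the connectivity measures are mediators. Call only the surviving paths significant, and give unadjusted intervals as description. Either restate the mediation power finding as unadjusted or redo it under the BH rule.
- **If mediation is exploratory:** remove the significance wording from the interval rule and report the intervals as unadjusted and descriptive.

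Either change takes a sentence or two. The first also needs a few lines of code, and a rerun of the power simulation if that option is chosen. No new data are needed. The downside of the first is that somewhat fewer paths will reach significance, in an analysis that the plan already describes as limited in power.

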Power Analysis for the Mediational Analysis: To assess power to detect mediation, we performed a Monte Carlo-based power analysis using simulated data. We varied the parameter values to roughly correspond to Cohen's criteria for small, medium, and large effects. This resulted in a total of 27 conditions, which we examined at our target sample size of 200. Each condition was replicated 2000 times and we calculated empirical power, which we defined as the proportion of times out of 2000 where we rejected the null hypothesis at  $\alpha = .05$ . Given the exploratory nature of this analysis and to simplify the simulation for the power analysis, we omitted covariates and did not vary the effects for the other condition contrasts (i.e., they were always fixed to 0). Next, we fit a path model using the lavaan package in R.

Our findings suggest that in order to detect mediation, the effect of condition on the mediator must be large and the effect of the mediator on the outcome must be medium or large. In addition, if the effect of condition on the outcome is not large, but small or medium sized, then we will be underpowered and would likely conclude complete mediation, when mediation may only be partial or non-existent. Based on this power analysis, it is likely that the MDES for the moderated mediation models will need to be at least medium to large as well.

Missing data. Because we will replace participants who do not come in for session 2 after doing session 1 (which is rare in our experience), we should have 200 completed participants. Missing data, however, could arise from problems in obtaining good imaging data. Participants also often fail to fully complete questionnaires and/or refuse to provide information on household income. If there is missingness in any of the dependent or independent variables, multiple imputation will be used (Little & Rubin, 2014; Peng, Harwell, Liou, & Ehman, 2006; Schafer & Graham, 2002). Variables related to the missingness and the variables missing data will be included in the missing data model. In the event that missingness is not at random (MNAR), we will investigate the use of models for non-ignorable missing data.

**15.4 Data Integrity:** Questionnaire data will be double-entered to reduce the likelihood of errors in data entry. Biospecimen data will be assayed in labs

that have standard quality control procedures. MRI data reviewed for raw data quality and artifact detection.

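### The mediation plan forecasts that partial mediation would be called complete when the effect of condition on the outcome is small or medium, and sets no rule to prevent it

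*Combined protocol and SAP*

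**What the plan says.** Hypothesis #2 (Section 2.3) is that neural activity mediates the buffering of the physiological response. Section 15.3, under Mediational Analysis, examines this only when condition, or condition by pubertal status, shows differences both in brain activity and in cortisol or heart rate. Indirect effects get bias-corrected 95% intervals, and "confidence intervals that are non-overlapping with zero will be considered significant". That is the only decision rule given for mediation.

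The paragraph on power for the mediational analysis describes a simulation over a grid of Cohen-type effect sizes: "This resulted in a total of 27 conditions, which we examined at our target sample size of 200". There were 2000 replicates in each cell of the grid. For simplicity, "we omitted covariates and did not vary the effects for the other condition contrasts". Two results are reported:

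- For mediation to be detected, "the effect of condition on the mediator must be large and the effect of the mediator on the outcome must be medium or large".
- "if the effect of condition on the outcome is not large, but small or medium sized, then we will be underpowered", and the team "would likely conclude complete mediation, when mediation may only be partial or non-existent".

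Neither the path values nor any power figure is given. The text then turns to moderated mediation and missing data. Nowhere does the plan define complete or partial mediation, or say how the direct effect will be tested or reported.

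**The concern.** The plan predicts a wrong inference by its own team and leaves the way to it open. Low power on the path from condition to outcome can turn partial mediation into an apparent complete mediation only if a direct effect that fails to reach significance is read as no direct effect. That treats absence of evidence as evidence of absence, on the path for which the plan says power is short.

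At stake is the strength of the conclusion on Hypothesis #2. A report of complete mediation says that the measured brain activity accounts for the whole buffering effect on cortisol or heart rate. If a real direct effect was simply missed, that statement comes from the sample size. Disclosing the limitation in a power paragraph does not stop the label from appearing in the results.

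**Working it through.** **Inputs from the plan.** n = 200 and three arms (Section 5.1); possible loss of 40 to movement, leaving 160 (Section 15.2); alpha 0.05; no covariates and the other condition contrasts fixed at zero (Section 15.3).

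**Assumed.** Equal arms, two-sided tests, and all path values, since the plan gives none.

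**1. The plan's own result.** It is qualitative, so it can be matched only in pattern. With small/medium/large set to 0.14/0.39/0.59 for all paths and three arms, power for the indirect effect is 0.60–0.62 for a medium condition-to-mediator effect and 0.92–0.93 for a large one, when the mediator-to-outcome effect is medium or large. Direct-effect power is 0.12–0.18, 0.61–0.79 and 0.91–0.99 for small, medium and large effects. This agrees with the plan's statements. With 0.2/0.5/0.8 for the condition paths and 0.1/0.3/0.5 for the mediator path, it agrees less well: a medium condition-to-mediator effect already gives 0.81–0.83.

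**2. How often a real direct effect is missed.** Take condition to mediator a = 0.8, mediator to outcome b = 0.4, mediator residual SD 1, outcome residual SD s = √(1 − 0.4²) = 0.917. With m = n/3 per arm,

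SE(direct) = s × √(2/m + a²/(n − 3)).

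- n = 200: 0.917 × √(0.0300 + 0.64/197) = 0.167
- n = 160: 0.917 × √(0.0375 + 0.64/157) = 0.187

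The chance of non-significance is about Φ(1.96 − direct/SE):

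| True direct effect (SD) | n = 200 | n = 160 |
|---|---|---|
| 0.2 | Φ(0.76) = 78% | Φ(0.89) = 81% |
| 0.3 | Φ(0.165) = 57% | Φ(0.355) = 64% |
| 0.5 | Φ(−1.03) = 15% | Φ(−0.715) = 24% |
| 0.8 | Φ(−2.83) = 0.2% | not needed |

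Simulation at n = 200 gives about 78%, 57% and 16% for the first three rows. The indirect effect is detected in over 99% of those trials.

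**3. The entry condition.** Mediation is examined only if condition also affects the mediator and the outcome. The total effect on the outcome is direct + ab = direct + 0.32, with within-arm SD 1 and SE √(2/66.7) = 0.173. The chance of passing on the outcome is about Φ(0.52/0.173 − 1.96) = 85% at a direct effect of 0.2, Φ(0.62/0.173 − 1.96) = 95% at 0.3, and over 99% at 0.5. A trial that misses the direct effect is also likelier to fail this condition, so the joint share comes from simulation:

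| True direct effect (SD) | Labelled complete, n = 200 | Labelled complete, n = 160 |
|---|---|---|
| 0.2 | about 63% | about 57% |
| 0.3 | about 51% | about 52% |
| 0.5 | about 16% | about 23% |
| 0.8 | well under 1% | not needed |

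These move by a few percentage points with simulation error and with how the entry condition is tested.

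**4. Range over assumed paths (n = 200, entry condition not applied).** Among trials with a significant indirect effect, the share with a non-significant direct effect is 74–94% when the direct effect is small. It is about 9–46% when medium with three arms (19–62% with four, run because Section 15.1 still mentions four buffering conditions), and 0–22% when large.

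**5. Mediation truly absent.** A claim of mediation then needs a false-positive indirect effect. Across the cases run, this happened in up to about 7% of trials, against a nominal 5%. The complete label followed in about 0.1–5% of trials before the entry condition. After it, with b = 0, the figure was under 1%.

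**The case against.** The strongest reply is that the plan contains no faulty rule. A reader might infer from the forecast that the analysis plan equates a non-significant direct effect with none. The documents do not say so: the only rule is the indirect-effect interval, the reason given for the forecast is low power, and the complete/partial distinction appears only in that caveat. This stands. The mechanism described here is an inference, though it is hard to see how else low power could produce the predicted label when mediation is partial.

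A reader might also infer that the error is likely whatever the effect size. The plan limits its warning to small and medium effects, and the figures agree: with a large direct effect the error is uncommon, and with a medium one the word likely depends on the assumed paths.

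A third tempting reading is that the study would probably claim mediation where there is none. The plan's wording invites it, but its own interval rule contradicts it.

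It is also fair that the authors disclose the limitation, call the analysis exploratory and keep it apart from the primary analyses, and that basing mediation on the indirect-effect interval is already the plan. None of this supplies the missing piece, a statement of what may be concluded when the direct effect is not significant.

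**Conclusion.** The concern holds in a limited form. For a small or medium effect of condition on the outcome, the plan forecasts that partial mediation would be reported as complete, and nothing in it prevents that. Under the assumed paths, the label would be wrong in about half to two-thirds of trials for direct effects of 0.2–0.3 SD, and in about one in six at 0.5 SD with 200 children or about one in four with 160. These sizes rest on assumed path values, equal arms, no covariates, and the inferred reading of a non-significant direct effect. The plan also leaves open whether its effect of condition on the outcome means the direct or the total effect; the direct effect is used here.

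The forecast's reference to absent mediation is unsupported and should not be carried forward. The primary regression analyses, the sample size and the indirect-effect test are unaffected. The change should be made because mediation is a named hypothesis and the plan itself predicts the error.

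**What to change.** In Section 15.3:

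1. Keep the bias-corrected interval for the indirect effect as the only basis for a mediation conclusion.
2. Add that the direct effect will be reported beside it with its 95% confidence interval.
3. Replace the forecast in the power paragraph with a rule that mediation will not be called complete on the basis of a non-significant direct effect. Apply the same rule to the moderated mediation models.
4. Remove the reference to absent mediation, or explain how it could arise given the interval rule.
5. Say whether the effect of condition on the outcome is the direct or the total effect, and give the path values and power figures from the simulation.

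The cost is wording, plus printing simulation inputs and results that the team should already hold. No new data are needed, and the design and sample size do not change.
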